12. PLANS FOR COMMUNICATION OF STUDY RESULTS

Pfizer and the scientific committee undertake to send the study results to all the doctors participating in the study.

At least one communication and one publication are planned at the end of the study.

12.1. Scientific Committee

A qualified scientific committee was set up for this study. It is composed of 2 doctors specialized in gastroenterology, who participated in drafting the protocol and its validation, and who will take part in the validation of the statistical analysis plan and drafting the clinical report. The scientific committee is also responsible for proposing and/or validating changes to the protocol once the study is underway.

12.2. Access to source data

A source document is any original document or object that proves the existence or accuracy of a data or fact recorded during the research and in particular the medical records of included patients.

The investigators will make available the documents and individual data strictly necessary for data collection during the study, study monitoring, quality control and auditing of the study, to the persons with access to these documents in accordance with legislative and regulatory provisions (Articles L.1121-3 and R.5121-13 of the Code of Public Health).

12.3. Confidentiality

Pursuant to current legislation (Articles L.1121-3 and R.5121-13 of the Code of Public Health), persons with direct access to source data must take all the necessary precautions to ensure the confidentiality of information about the experimental drugs, the research and participating subjects, in particular as regards their identity and the results obtained. These persons and the investigators themselves are subject to professional secrecy.

During the study or after its completion, the data collected on the participants and sent to the sponsor by the investigators (or any other specialized persons involved) will be made anonymous. They should in no case show the names of the persons concerned or their address.

No nominative data about the patient will be collected.

The sponsor (or its representative) must ensure that each person participating in the research gives his/her agreement for access to his/her personal data which are strictly necessary for the quality control of the research.

12.4. Data ownership

PFIZER will retain ownership of all the case report forms, data analysis, and reports resulting from this study.

12.5. Communication and publication

All the information obtained from this study will be considered confidential, until Pfizer and the members of the scientific committee have carried out its analysis and final review.

The study results may be published or presented by the members of the scientific committee after revision and approval by Pfizer, who will ensure that confidential information or industrial property are not disclosed. Before publication or presentation, a copy of the final text should be sent by the member(s) of the scientific committee to Pfizer, for comment. Such comments aim to ensure the scientific content of the proposed publications and/or presentations and make sure that the data and the material referring to Pfizer products and activities receive a fair, accurate, and reasonable presentation.

12.6. Communication of problems

If a prohibition or restriction is imposed (for example, the suspension of the study) by a responsible competent authority in any region of the world, or if the investigator becomes aware of any new information that could affect the evaluation of the benefits and risks of a Pfizer product, Pfizer must be immediately informed.

Moreover, the investigator shall immediately inform Pfizer about all the urgent safety measures taken by the investigator to protect study patients from any immediate danger, and from all the serious breaches of this non-interventional study protocol about which the investigator is aware.

14. LIST OF TABLES

Table 1: Evaluation of response to treatment considering outcome of DAS28 (EULAR criteria)

Table 2: Planned Study Schedule

Table 3: Patients data collected

Table of adverse events

15. LIST OF FIGURES

Figure 1: Study schema

Figure 3 : Potential predictive factors of drug survival

ANNEX 1. LIST OF INDEPENDENT DOCUMENTS

Numéro	Numéro de référence du document	Date	Titre
1	1.2	09-NOV-2018	Patient Information Leaflet
2	2.0	21-DEC-2020	Case Report Form including non-inclusion log and adverse event reporting form
3.1	PCS		PCS – Pain Catastrophizing Scale
3.2	CSQ		CSQ – Coping Strategies Questionnaire
3.3	GIRERD		GIRERD
3.4	FIRST		FiRST-Fibromyalgia Rapid Screening Tool
3.5	Euro QoL		Euro QoL EQ-5D -3L
3.6	SF-12 (Version 2)		SF-12 (Version 2)
3.7	FACIT-F		FACIT-F - Functional Assessment of Chronic Illness Therapy-Fatigue
4	NA	08-DEC-2020	Sites list

ANNEX 2. ADDITIONNAL INFORMATION

Not Applicable

1 AMENDMENTS FROM PREVIOUS VERSION(S)

1.1 VERSIONS

Version	Effective Date	Change Type (New, Revise, Admin)	Summary of Revisions
1	11-Dec-2019	New	
2	25-Feb-2020	Revise	To add subgroup analyses and to include comments from the scientific committee.
3	26-Apr-2021	Revise	To be in line with protocol amendment 2 To modify the definition of the Full Analysis Set To assess the impact of Covid-19 on study results

1.2 AMENDMENTS FROM THE PROTOCOL

The handling of visit windows has been amended in the SAP compared to the protocol. The Protocol states that:

In order to collect comparable study data, visits 2 to 9 occurring +/- 14 days of the scheduled visit date will be used for data analysis.

As the visits will be scheduled according to clinical practice there are likely to be many visits outside of the windows defined in the protocol. To ensure the primary analysis incorporates all visits at which a patient might experience a treatment escalation all visits will be included for the primary analysis, based on the windowing in [Table 9](#) of Section [11.1](#).

2 INTRODUCTION

Note: in this document any text taken directly from the non-interventional (NI) study protocol is *italicised*. This SAP is based on A3921313 NIS DeFacTo Final Protocol, dated 09 November 2018.

Rheumatoid arthritis (RA) is an auto-immune disease characterised by inflammation and joint destruction which is at the origin of progressive incapacity and negative psychological effects ^(1, 2). RA is a problem of public health, whether on the level of the individual or on society, in particular, regarding incapacity for work and resultant loss of productivity ^(3, 4).

According to the recent European League Against Rheumatism (EULAR) recommendations ⁽⁵⁾ and the current recommendations of the French Society of Rheumatology (SFR) ⁽¹⁾, earlier diagnosis is leading to earlier therapeutic intervention

with the goal of disease activity control, maintenance of physical function, optimization of quality of life and improvement of patient mindset⁽¹⁾. “Treat-to-target” is defined as the basic therapeutic principle in order to reach a goal of sustained remission or low disease activity in every patient^(1, 5).

Xeljanz® (Tofacitinib) is an orally targeted synthetic DMARDs (ts-DMARDs) of the new class called Janus kinase inhibitors (JAK-inhibitors). In combination with methotrexate (MTX), Tofacitinib has been approved in 2017 by the European Medicine Agency (EMA)⁽⁶⁾ for the treatment of moderate-to-severe active rheumatoid arthritis in adult patient who have responded inadequately to, or who are intolerant to one or more disease modifying anti-rheumatic drugs (DMARDs). Furthermore, Tofacitinib can also be administered as monotherapy in case of intolerance to MTX or when treatment with MTX is inappropriate^(7, 8)

Tofacitinib efficacy and safety in the treatment of rheumatoid arthritis has been proven and tried not only across a wide clinical development plan including 7 phase III studies and 2 long-term extension studies^(7, 9-15, 16), but also under real life conditions of use since its first approval in the United States in 2012 and subsequent years in other countries worldwide⁽¹⁷⁾.

Although the efficacy and safety profile of Tofacitinib is currently well-documented in the clinical setting^(7, 9-15, 16), many fields of research remain to be investigated regarding this drug of a novel therapeutic class, including outcomes in the real world setting. For example, nowadays it is recognized that treatment retention is an overall marker of treatment success depending on multiple factors including efficacy, safety, patients' and disease characteristics at baseline, patients' and physicians' confidence with the treatment^(1, 5). Survival rate is a standardized method for identifying predictive factors of drug survival. Existing data with biologic DMARDs in rheumatoid arthritis have identified a number of independent predictors for treatment continuation⁽¹⁸⁻²³⁾. Regarding Tofacitinib, newly introduced on the market, few data on drug retention⁽²⁴⁾ and no data on the factors predictive of Tofacitinib drug survival in patients with RA are available.

Therefore, the primary objective of the DeFacto study will be to identify the factors predictive of Tofacitinib drug survival in patients with RA.

Moreover, rheumatoid arthritis substantially affects quality of life. Different factors such as pain, disability or fatigue which are directly or indirectly the result of inflammation can have a negative impact on quality of life^(1, 25). Nevertheless, such quality of life is not governed solely by symptoms of the disease, but also by the behaviour of the patient, as well as by behavioural strategies which he/she evidences with regard to the disease. We often refer to catastrophisation⁽²⁶⁻²⁸⁾ and coping⁽²⁹⁻³²⁾ to evaluate these behavioural strategies. If catastrophisation is described as a distortion of the perception of pain involving a both emotional and cognitive component, pushing the patient to see only the worst⁽²⁶⁻²⁸⁾, coping involves adaptive strategies by which the patient attempts to find solutions in order to better cope with his/her disease⁽²⁹⁻³²⁾. It has been demonstrated that

such behavioural strategies can influence directly or indirectly the intensity of symptoms⁽³³⁾.

As secondary objectives, the impact of behavioural strategies on drug survival and other clinical parameters as well as Tofacitinib effectiveness and tolerability will be studied under real-life conditions of use in French patients with RA.

2.1 STUDY DESIGN

This is an observational, open-label, prospective, multi-centre, national study designed to evaluate the factors predictive of Tofacitinib's survival in patients with rheumatoid arthritis.

The study will consist of 500 patients recruited from approximately 100 centres. The duration of this study will be approximately 48 months including a 24-month recruitment period and a 24-month patient follow-up period. Patients will be followed prospectively and follow-up visits will be conducted after the initial consultations. No visit or additional test is required by the protocol, since the study is observational: the modalities for follow-up and treatment will be left up to the sole judgement of the participating doctor. Figure 1 shows the study schema.

Data from France will be compared and also pooled with data from other countries. Details will be included in a separate analysis plan for a pooled analysis.

[figure not shown]
Figure 1: Study schema

Table 1 shows the schedule of activities.

Table 1 Schedule of Activities

	Inclusion visit Initiation of treatment (Target Day: 1)	Follow-up visit						Additional visit in case of discontinuation of Tofacitinib outside the 6 scheduled visits
		At 1 month (V1) (Target Day: 30)	At 3 months (V2) (Target Day: 91)	At 6 months (V3) (Target Day: 183)	At 12 months (V4) (Target Day: 365)	At 18 months (V5) (Target Day: 548)	At 24 months (V6) (Target Day: 731)	
Patient consent	X							
Verification of eligibility criteria	X							
Demographic characteristics								
Age, gender	X							
Weight, height, BMI	X							
Smoking status	X							
Alcohol intake (excessive use M>3 glasses wine/day, F>2 glasses wine/day)	X							
socio-educational status lives alone (Y/N)	X							
Status with respect to hepatitis B	X							
Status with respect to hepatitis C								
Status with respect to tuberculosis								
Vaccine status - Pneumococcus								
- Herpes zoster	X							
History of chickenpox (Y/N)								
Biological parameters at inclusion								
Haemoglobin (g/dl)	X							
Mean corpuscular volume (μ ³)	X							
Lymphocyte absolute count (cells/mm ³)	X							
Neutrophil absolute count (cells/mm ³)	X							

	Inclusion visit Initiation of treatment (Target Day: 1)	Follow-up visit						Additional visit in case of discontinuation of Tofacitinib outside the 6 scheduled visits
		At 1 month (V1) (Target Day: 30)	At 3 months (V2) (Target Day: 91)	At 6 months (V3) (Target Day: 183)	At 12 months (V4) (Target Day: 365)	At 18 months (V5) (Target Day: 548)	At 24 months (V6) (Target Day: 731)	
Characteristics of RA								
Date of initial diagnosis	X							
Age at time of diagnosis of disease	X							
Erosions at time of diagnosis (Y/N)	X							
Rheumatoid nodules (previous or current): Y/N	X							
Secondary Sjögren Syndrome (Y/N)	X							
RF (negative, positive < 3x N, positive + \geq 3x N)	X							
ACPA (negative, positive < 3x N, positive + \geq 3x N)	X							
Previous treatments of RA (treatment line)	X							
If MTX as 1 st line treatment (just before prescription of Tofacitinib), dosage and route of administration (PO /SC)	X							
Evaluation of RA								
Existence of comorbidities: - CV disease - Cancers - Infection - Gastro-intestinal disease - Osteoporosis - Depression - Diabetes	X							

	Inclusion visit Initiation of treatment (Target Day: 1)	Follow-up visit						Additional visit in case of discontinuation of Tofacitinib outside the 6 scheduled visits
		At 1 month (V1) (Target Day: 30)	At 3 months (V2) (Target Day: 91)	At 6 months (V3) (Target Day: 183)	At 12 months (V4) (Target Day: 365)	At 18 months (V5) (Target Day: 548)	At 24 months (V6) (Target Day: 731)	
Chronic low back pain (Y/N)	X							
Existence of fibromyalgia (FiRST questionnaire)	X	X	X	X	X	X	X	X
ESR (min/hour)	X	X	X	X	X	X	X	X
CRP (mg/mL)	X	X	X	X	X	X	X	X
PtGA (patient)	X	X	X	X	X	X	X	X
PhGA (physician)	X	X	X	X	X	X	X	X
Evaluation of pain by the patient	X	X	X	X	X	X	X	X
Duration of morning stiffness	X	X	X	X	X	X	X	X
TJC (28)	X	X	X	X	X	X	X	X
SJC (28)	X	X	X	X	X	X	X	X
PCS Questionnaire	X	X	X	X	X	X	X	X
CSQ Questionnaire	X	X	X	X	X	X	X	X
GIRERD Questionnaire	X	X	X	X	X	X	X	X
Euro QoL EQ-5D-3L Questionnaire	X	X	X	X	X	X	X	X
SF-12 Questionnaire	X	X	X	X	X	X	X	X
FACIT-fatigue Questionnaire	X	X	X	X	X	X	X	X
Administration of Tofacitinib								
Reason for initiation of Tofacitinib (problem of tolerability to previous treatment, primary failure (absence of significant improvement), secondary failure (significant improvement and then loss of efficacy), patient choice, other	X							
Dosage	X	X	X	X	X	X	X	X
Concomitant treatments								

	Inclusion visit Initiation of treatment (Target Day: 1)	Follow-up visit						Additional visit in case of discontinuation of Tofacitinib outside the 6 scheduled visits
		At 1 month (V1) (Target Day: 30)	At 3 months (V2) (Target Day: 91)	At 6 months (V3) (Target Day: 183)	At 12 months (V4) (Target Day: 365)	At 18 months (V5) (Target Day: 548)	At 24 months (V6) (Target Day: 731)	
Conventional synthetic DMARD: INN, dosage, date of start	X	X	X	X	X	X	X	X
Corticosteroid therapy: dose, p.o./bolus dose	X	X	X	X	X	X	X	X
Psychotropic treatment (antidepressant, BZD, BZD hypnotic)	X	X	X	X	X	X	X	X
Changes to treatment with Tofacitinib								

 - Y/N - If yes: date of change, dosage, reasons for change 		X	X	X	X	X	X	X
Discontinuation of treatment with Tofacitinib								

 - Y/N, - If yes: date of discontinuation and reasons for discontinuation - Prescription of a biologic treatment or tsDMARD: Y/N. If yes: INN, dosage and date of start 		X	X	X	X	X	X	X
Safety								
Collection of AEs		X	X	X	X	X	X	X

2.2 STUDY POPULATION

Patients eligible for this study can be included by the physician if they are starting a treatment with Tofacitinib for RA according to usual clinical practice and satisfy all of the criteria for inclusion. Patient treatment is independent from patient enrolment into the study.

Data will be recorded during the 24 months participation of each patient. Visits, target dates and windowing is described in [Table 9](#), Section [11.1](#).

Patients will be followed prospectively and follow-up visits will be conducted after the initial consultations. No visit or additional test is required by the protocol, since the study is observational: the modalities for follow-up and treatment will be left up to the sole judgement of the participating doctor.

In case of discontinuation of treatment with Tofacitinib, for whatever reason, clinical data will be collected as close as possible to the date of such a discontinuation. Likewise, in case of Tofacitinib discontinuation outside the 6 scheduled visits, an additional visit to collect clinical data as close as possible to the date of this discontinuation should be organised.

Eligible patients will be followed starting from the date of the first prescription of Tofacitinib during 24 months, whether they continue treatment with Tofacitinib or not.

In order to ensure expected recruitment, the study will be conducted by about 100 rheumatologists. Participating physicians will be selected from among those all over France out of the total number of French health institutions which manage patients with rheumatoid arthritis.

In order to reach an objective of participation of 100 centres desired, the study will be offered to about 550 centres.

2.3 TREATMENT LABELS

The treatment labels for analyses are as follows:

Treatment	Treatment Label
Tofacitinib as monotherapy	Tofacitinib as Monotherapy
Tofacitinib as combination (with MTX or other csDMARDs)	Tofacitinib as Combination
Tofacitinib in total	Total

Each treatment group (Tofacitinib as Monotherapy or Tofacitinib as Combination) will correspond to patients who received a given treatment for at least 80% of their follow-up. The total group will include all patients enrolled in this study and took at least one dose of Tofacitinib. Note: due to the criteria for each treatment group the total column may not

equal the number in Tofacitinib as Monotherapy plus the number in Tofacitinib as Combination.

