9.1.4. Follow-up visits of patients

Patients will be followed in the setting of the study over a maximum 24-month duration or up to their early withdrawal from the study for whatever reason.

At each follow-up visit (1 month (V1), 3 months (V2), 6 months (V3), 12 months (V4), 18 months (V5), 24 months (V6) and at time of withdrawal from the study), the physician must do the following:

- complete the questionnaire corresponding to the follow-up visit,
- give the patient the PCS, CSQ, FiRST, GIRERD, EuroQoL EQ-5D-3L, SF-12, FACIT-Fatigue questionnaires.

The patient must complete these questionnaires and give them back to his/her physician at the end of each visit.

The patient paper questionnaires will be recovered by a carrier who will deliver them to Pfizer and they will be transferred by Pfizer electronically via a secure website to the firm in charge of data management for data entry. During this period, physicians make a commitment for comprehensive and regular collection of follow-up data for each patient enrolled.

Total duration of follow-up for a patient will be a maximum of **24 months**.

Total duration of the study will be **48 months**.

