3 INTERIM ANALYSES

Interim analyses will be planned each year. These interim analyses will be performed on the available data. They will be purely descriptive and will include the analyses planned in this SAP except multivariate analyses and correlation assessments. Outputs required will be highlighted in the study List of Tables.

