Hazard ratios (HRs) and the 95% confidence intervals (CIs) will be created and displayed, along with the associated p value from the models. All statistical tests will be two-sided with alpha of 0.05, apart from during variable selection using univariate models for the primary analysis, where alpha will be considered as 0.1. Two-sided CI's will be presented whenever it is appropriate. No adjustment for multiplicity will be used.

Drug survival with Tofacitinib will be described with the Kaplan-Meier (KM) method, using the SAS procedure PROC LIFETEST. Confidence intervals will be displayed, using the Klein and Moeschberger method. An estimate for drug survival at 12 and 24 months will be presented. A KM plot will be created to display the survival function of the Tofacitinib Total group. As a sensitivity comparison a KM plot will also be presented showing the Tofacitinib as Monotherapy group and the Tofacitinib as Combination Therapy group.

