8.2.3 Primary Analyses

The primary endpoint, duration of Tofacitinib drug survival, will be analysed using the FAS and the methods described in Section 8.1.1.1 Cox Proportional Hazards. The Tofacitinib drug survival tables will present a single Tofacitinib Total column, using the treatment label seen in Section 2.3. A Kaplan-Meier plot will present the survival function for Tofacitinib Total group. As a comparison, a second KM plot will present the

survival functions for both Tofacitinib as Monotherapy and Tofacitinib as Combination groups. The treatment labels seen in Section 2.3 will be used.

The list of potential predictive factors to include in the model for the primary analysis is seen in [Figure 2](#). Note: the factors seen in Figure 2 are all baseline predictors. Where SF-12 is considered within [Figure 2](#), the 8 health domains as well as PCS_{SF12} and MCS will each be considered as potential predictive factors. As PCS_{SF12} and MCS are linear combinations of the 8 health domains, collinearities are anticipated, however considering all of them as potential predictors will allow us to investigate which domains contribute the most to PCS_{SF12} and/or MCS. If necessary, transitional models will be investigated including separately component summary measures (PCS_{SF12} and MCS) and the 8 health domains.

Figure 2: Potential predictive factors of drug survival

In the event of missing data, see Section 7.1. Missing data methods will be performed on the final multivariate Cox PH model, and not for the individual univariate models.

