8.2.4 Sensitivity Analyses

Sensitivity analyses, except where specified, will use the FAS. All sensitivity analyses tables will present a single Tofacitinib Total column, using the treatment label seen in Section 2.3. All sensitivity analyses plots will present Tofacitinib as Monotherapy and Tofacitinib as Combination, using the treatment labels seen in Section 2.3.

Complete Case Analysis

In the event of more than 10% missing data in baseline covariates then a complete case analysis will take place, using the methods described in Section 7.2.

Random Survival Forests

Random survival forests will be created as a sensitivity analysis to complement the standard Cox PH model, as described in Section 8.1.1.2 Random Survival Forests, and will consider the potential predictive factors seen in Figure 2 in Section 8.2.3. In the event of missing data, see Section 7.3.

DAS28-4 CRP at Month 3 as a Potential Predictive Factor

8.2.5 As part of the sensitivity analyses, DAS28-4 CRP at month 3 will be considered as an additional potential predictive factor along with the factors seen in Figure 2 in Section 8.2.3, and will follow the methods described in Section Analysis of 8.1.1.1 Cox Proportional Hazards. This will use the Month 3 Analysis Set. In the event of missing data, follow Section 7.1.

The methods for random survival forests, described in Section 8.1.1.2 Random Survival Forests, will also be repeated including DAS28-4 CRP at month 3 as a potential predictive factor, along with the factors in Figure 2 in Section 8.2.3. This will use the Month 3 Analysis Set. In the event of missing data, follow Section 7.3.

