8.2.6 Secondary Analyses

All secondary analyses will use the FAS. Secondary analyses will consider Tofacitinib Total as the treatment group. Summaries of secondary endpoints will be presented for Tofacitinib total, Tofacitinib as monotherapy and Tofacitinib as combination, using the treatment labels seen in Section 2.3.

Each endpoint will apply the specific rules for missing data as described in Section 7 but if there are missing data points after this, no missing data methods will be used to impute data for the secondary analyses.

All the analyses described hereafter in this section will be performed on all assessments collected before permanent Tofacitinib discontinuation (On-Treatment Analysis). In addition, analyses described in sub-sections 8.2.6.2, 8.2.6.3, 8.2.6.4 and 8.2.6.5 will be re-run on all available data including retrieved dropout data (Analysis on All Available Data).

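### The Monotherapy and Combination groups require at least 80% of follow-up on the regimen, which removes early tofacitinib stoppers from the by-regimen survival plot

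*SAP*

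**What the plan says.** SAP 2.3 sets three labels: Monotherapy, Combination (with methotrexate or another csDMARD) and Total. The first two "will correspond to patients who received a given treatment for at least 80% of their follow-up". The section notes that they may not add up to Total, but not which patients will be missing. It does not define follow-up.

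Elsewhere, follow-up is time in the study. SAP 2.2 follows patients from first prescription "during 24 months, whether they continue treatment with Tofacitinib or not". Protocol 9.1.4 follows them "over a maximum 24-month duration or up to their early withdrawal from the study for whatever reason". SAP 8.2.1 provides for patients who stop tofacitinib and remain in the study, by listing their later treatments.

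The event in SAP 6.1.1.1 is permanent discontinuation of tofacitinib. The labels are used in these places:

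- SAP 8.2.3: a second Kaplan-Meier plot of the "survival functions for both Tofacitinib as Monotherapy and Tofacitinib as Combination groups". SAP 8.1.1.1 calls it a sensitivity comparison.
- SAP 8.2.4: "All sensitivity analyses plots will present Tofacitinib as Monotherapy and Tofacitinib as Combination".
- SAP 8.2.6: "Summaries of secondary endpoints will be presented for Tofacitinib total, Tofacitinib as monotherapy and Tofacitinib as combination".
- SAP 3: the yearly interim analyses "will include the analyses planned in this SAP except multivariate analyses and correlation assessments".

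**The concern.** The plot shows time to stopping tofacitinib, but a patient enters either curve only by having been on the regimen for most of follow-up. When follow-up continues after the stop, an early stopper cannot reach 80% on any regimen and drops out of both curves, taking the event along. A stopper who leaves the study at the stop has 100% on the regimen and is kept. Selection therefore acts on the outcome and on study withdrawal together.

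By-regimen drug survival would look better than it is, beside a Total curve that includes every event. The secondary summary columns are affected even early on: the month-3 on-treatment column omits patients who were on drug at month 3 but stopped later. The all-available-data re-run in SAP 8.2.6 is meant to include retrieved dropout data, yet the patients who supply such data are largely those the rule removes from the regimen columns.

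Labels can also change over time. A patient who stops at month 10 and stays has 10/12 = 83% at a data cut 12 months after starting, and 10/24 = 42% at month 24. The patient is classified at the first and not at the second.

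**Working it through.** **Inputs.** Follow-up of 24 months (Protocol 4 and 9.1.4; SAP 2.2). Threshold of 80% (SAP 2.3). Drug survival of 50% at 24 months and about 300 patients (Protocol 9.5). Assumptions not in the documents: constant hazard, no csDMARD change while on tofacitinib, no other loss to follow-up, follow-up means time in study, and both regimen groups taken together. A share f of stoppers leaves at the stop; the rest stay to month 24. The documents do not give f, so a range is shown.

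**The plan's own figure.** 50 × 0.3 = 15 variables; 15 × 10 = 150 events; 150 / 0.50 = 300 patients. Protocol 9.5 is reproduced.

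**Cut-off.** 0.8 × 24 = 19.2 months (0.8 × 731 = 584.8 days).

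**Early stoppers.** With S(t) = 0.5^(t/24), the share stopping before month 19.2 is e = 1 − 0.5^0.8 = 0.4257. That is 0.4257 × 300 = 128 patients, or 0.4257 / 0.5 = 85% of all stoppers.

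**What the by-regimen outputs show.**

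- Unclassified: e(1 − f)
- Retention shown at 24 months: 0.5 / [1 − e(1 − f)]
- Retention shown at 12 months: 1 − f(1 − 0.5^0.5) / [1 − e(1 − f)]
- On drug at month 3 but in neither column: (1 − f)(0.5^(3/24) − 0.5^0.8) / 0.5^(3/24)

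| Stoppers who leave at the stop (f) | Unclassified, of 300 | Shown at 12 months (true 70.7%) | Shown at 24 months (true 50%) | On drug at month 3, in neither column |
|---|---|---|---|---|
| 0% | 42.6% (128) | 100% | 87% | 37% |
| 50% | 21.3% (64) | 81% | 64% | 19% |
| 70% | 12.8% (38) | 76% | 57% | 11% |
| 100% | 0% (0) | 70.7% | 50% | 0% |

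A simulation of 400,000 patients under the same assumptions agrees within 0.2 percentage points.

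**Curve shape (f = 0).** Keeping S(24) = 0.50, linear accrual of events gives 120 patients lost (80% of events) and 83% shown at 24 months. A Weibull curve with shape 1.3 gives 121 (81%) and 84%; shape 0.7 gives 134 (89%) and 90%.

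**True retention other than 50%.** For 40%, 60% and 70% at 24 months, the plot shows 83%, 90% and 93% with f = 0 (52%, 34% and 25% unclassified), and 54%, 72% and 80% with f = 0.5.

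**Shorter follow-up.** The cut-off is 80% of the patient's own follow-up. A stop at month 12 with exit at month 14 gives 12/14 = 86% and is kept; exit at month 16 gives 12/16 = 75% and is lost.

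**The case against.** The strongest counter-argument is that follow-up is undefined in SAP 2.3 and might mean time on tofacitinib. SAP 8.1.1.1 does use the term for the survival time that is censored at the last visit. On that reading most stoppers are classified and the loss of early events largely disappears. This stands as a possible intention, but SAP 2.3 does not say it, and SAP 2.2 describes follow-up as running on after tofacitinib stops. Even on that reading, membership would depend on csDMARD changes made after baseline; the documents give no rates from which to size that bias.

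Second, the consequence is limited, and this stands. No objective compares the regimens (SAP 2.4), there are no formal hypotheses (SAP 4), and the plot is a sensitivity comparison. The drug-survival tables have a single Total column (SAP 8.2.3), so the sentence "An estimate for drug survival at 12 and 24 months will be presented" does not promise by-regimen estimates; the distortion is in what the plotted curves show at those times.

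Third, the month 19.2 cut-off holds only for a patient followed the full 24 months, and the size ranges down to zero as f approaches 100%. Both are true. But the SAP provides for stoppers who remain in the study, so f = 100% is not the planned situation.

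Fourth, whether interims include by-regimen outputs depends on a separate list of tables. The example of changing labels applies only if they do.

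**Conclusion.** The concern holds. Under the SAP's text, membership of the two regimen groups depends on the event being plotted, and the by-regimen Kaplan-Meier plot overstates drug survival whenever early stoppers remain in the study. At the protocol's 50% retention with a constant hazard and no csDMARD change, it would show about 87% at 24 months if all stoppers stay, 64% if half stay, 57% if 30% stay, and the correct 50% only if none stay. The direction rests on reading follow-up as time in study; the size rests mainly on the unknown share who leave at the stop, and curve shape matters less. The by-regimen sensitivity plots and secondary columns carry the same selection. The primary Cox model, the Total Kaplan-Meier curve, the safety outputs and the behavioural Cox models use Total and are not affected. The rule should be changed, but it does not threaten the primary objective.

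**What to change.** In SAP 2.3, define Monotherapy and Combination by csDMARD co-treatment at V0, and use these labels for the by-regimen Kaplan-Meier plot, the sensitivity plots, the secondary summaries and any by-regimen interim outputs. Every patient with recorded V0 co-treatment is then classified, all of their events stay in the plot, and the label does not change between data cuts. The two groups sum to Total except for patients with no V0 record, who should be counted separately. State in the same sentence how a csDMARD that is being stopped at tofacitinib initiation is counted.

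The cost is SAP wording only. csDMARD use is recorded at inclusion (SAP 2.1, Table 1), and SAP 8.2.6.5 already lists concomitant csDMARD (yes/no) as a baseline characteristic. The small downside is that the label describes the regimen started and does not reflect later csDMARD changes.
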